### **6.1.1 Treatment of Outliers**

Individual concentration-time points, if considered anomalous, may be excluded from the analysis at the discretion of the pharmacokinetics following a review of the available documentation. Any such exclusion will be discussed with the sponsor and clearly outlined in the study report.

Entire individual study drug profiles for a subject may be excluded following review of the available documentation and discussion with the sponsor. However, results of analysis with and without the excluded profiles may be presented in the study report. Any such exclusion will be clearly listed in the study report along with justification for exclusion.

Any anomalous concentration values observed at predose will be identified and discussed in the CSR. Pharmacokinetic parameters will be computed if the predose concentration value is not greater than 5% of  $C_{max}$  for a given patient. If the predose concentration value is greater than 5% of the subsequent  $C_{max}$ , concentration and the PK parameter data for the given subject will be listed but excluded from the PK summaries and statistical analysis. The analysis may be repeated with and without these subjects as deemed appropriate.

### **6.1.2 Non-Quantifiable Concentrations**

All concentration values reported as no results (not collected or not determined) values will be treated as missing. For the calculation of concentration summaries, all concentrations below the quantifiable limit (BLQ) will be treated as zero. For the purpose of calculating summary statistics and plotting mean and individual concentration time profiles, BLQ values will be treated as zero prior to the first measurable concentration. After the first measurable concentration, subsequent BLQ values will be treated as missing. Descriptive statistics at any point will only be calculated if at least 2/3 of the individual data were measured and were quantifiable.

## **6.2 Immunogenicity**

Immunogenicity will be assessed by the development of antibody titers. The presence of ADA will be evaluated over the course of the post-injection period.

## 7. STATISTICAL METHODS

### 7.1 General

The statistical analysis will be conducted following the principles specified in the International Council for Harmonization (ICH) Topic E9 Statistical Principles for Clinical Trials (CPMP/ICH/363/96).

All statistical analyses will be performed using the statistical software SAS GRID Linux/SAS Studio and any exceptions will be detailed in the CSR.

All results collected in the database will be presented in listings. Both observed values and change-from-baseline values for each subject will be given where applicable. All continuous data will be listed with the same precision as presented in the database. Cohort, Subject ID, treatment and visit will be used to sort data listings.

Unless otherwise noted, continuous variables will be summarized using number of non-missing observations (n), arithmetic mean (mean), standard deviation (SD), median, minimum, maximum, lower quartile and upper quartile; categorical variables will be summarized using the frequency count and the percentage of subjects in each category.

In the data listings, study day relative to the study product dosing date for each cohort may be presented. Study day relative to dose will be calculated as: event date – study product dose date (+ 1 if event date  $\geq$  dose date).

All subjects who received placebo in each of the cohorts will be combined and presented along with the other dose levels until specified otherwise.

Baseline will be the latest available measurement prior to the study product dose date in each cohort.

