7.1. Visit 1: Screening (Day -28 to Day -3)

After providing written informed consent, each subject will be assigned a Subject ID number and undergo an eligibility assessment. The following will be done during the screening period (within 28 days prior to administration of study product). Results of screening tests and procedures will be evaluated by the investigator to determine eligibility prior to enrollment and randomization. The following procedures will be performed.

- Record demographics including age, gender, race and ethnicity. Obtain contact information.
- Obtain medical history. The medical history will include the following:
 - current medical diagnoses
 - past medical diagnoses
 - hospitalizations
 - major surgical procedures
 - blood transfusions or immunoglobulin within the last 6 months
 - live vaccines within the last 28 days
 - killed vaccines within the last 28 days
 - *Subjects will be eligible to receive any authorized COVID-19 vaccine after they complete Study Day 8
 - blood donation within the last 56 days
 - allergic reactions
 - drug and/or alcohol use or dependence
 - receipt of investigational drug within the last 28 days
 - Receipt of monoclonal antibody in the past
 - Exposure to botulinum toxin in the past 4 months
- Review concomitant medication history, including all medications taken within the last 28 days
- Review current use of contraceptive methods and recent menstrual history (female subjects only)

- Perform abbreviated PE by licensed clinician listed on the Form FDA 1572 [examples include Medical Doctor, Nurse Practitioner and Physician's Assistant]
- Obtain height and weight and calculate BMI
- Take vital signs (systolic and diastolic blood pressure, pulse rate, and oral temperature)
- Obtain fasting blood samples for viral serology, clinical laboratory screening tests
- Obtain blood sample for serum pregnancy test for women of child bearing potential
- Obtain blood to assess NX02 antibody levels (Cohort 4 subjects only)
- Obtain urine sample for dipstick urinalysis and urine toxicology
- Obtain 12-lead ECG
- Perform Breathalyzer test for recent alcohol use
- Counsel on the avoidance of pregnancy for women of child-bearing potential
- Counsel on the avoidance of botulinum toxin, vaccines and drugs listed in section 6.8.

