7.2. Visit 2: Baseline (Day 0)

Subjects meeting inclusion/exclusion criteria will be admitted to the clinical unit the day of the injection and the following procedures will be performed prior to study drug administration:

- Review inclusion/exclusion criteria to ensure the subject remains eligible for enrollment
- Update medical history
- Review and update concomitant medications
- Perform abbreviated physical examination
- Obtain vital signs
- Perform Breathalyzer test to detect recent alcohol use
- For women, a urine hCG test will be done. The results must be confirmed to be negative before dosing
- Obtain urine sample for toxicology
- Obtain blood samples for
 - Baseline serum PK (prior to injection and at the completion of the injection and 2hr, 4hr, and 8 hr post dosing for subjects in Cohorts 1-3)
 - Baseline serum PK (prior to injection and at 6 hours post-injection for subjects in Cohort 4)
 - Serum sample to store for future use samples (for subjects who consent)
 - MNA (prior to injection for subjects in Cohorts 1-3)

- MNA (prior to injection and at 2 hours post-injection (optional) for subjects in Cohort 4)
- ADA (prior to injection for all subjects)
- Hypersensitivity panel
- Clinical Safety Labs
- Randomize the subject and obtain study product from the pharmacy
- Perform IM Administration of study product
- Assessment of AEs and SAEs after administration of study product
- The subject is eligible for discharge after all assessments have been performed, including the 8-hour post injection blood draw and there are no signs of anaphylaxis.

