10.3.3.2. Additional Safety Analyses

Vital signs, physical examinations, and clinical laboratory values, including change from baseline, will be summarized by dose cohort and control group.

Descriptive summary statistics for laboratory data at admission (baseline value) and each applicable post-injection visit, including change from the baseline value, will be calculated. Descriptive summary statistics for vital signs at screening (baseline value) and each applicable post-injection visit, including change from the baseline value, will be calculated. Shift tables, showing individual subject changes from baseline will be presented for laboratory parameters using toxicity grading (Appendix B). Subjects with Graded values of vital sign and laboratory parameters will be identified in listings.

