APPENDIX A: SCHEDULE OF EVENTS

Study Visit	Screening ¹	Baseline	03	04	05 Cohort 1-3 Only	06	07	08	09	10	11	12	13 / Early Term	14 Cohort 4 Only
Study Day (Window)	-28 to -3	0	24 hr	48 hr	72 hr	4	8±1	15±1	30±1	45±3	60±3	90±3	120±3	180±3
Review Inc/ Excl Criteria	X	X												
Review Medical History	X	X												
Review Contraception/menses	X													
Perform Abbreviated PE ³	X	X												
Perform Symptom-Directed PE ¹³		X	X	X	X	X	X	X	X	X	X	X	X	X
Obtain Vital Signs ⁴	X	X	X	X	X	X	X	X	X	X	X	X	X	X
Obtain Screening Labs ⁵	X													
Obtain Clinical Safety Labs ⁶		X				X	X	X					X ¹⁸	X
Serum β-HCG	X ⁷													
Urine pregnancy test		X			X				X				X ¹⁸	X
Urine Dipstick ⁸	X	X											X ¹⁸	X
Urine Toxicology	X	X												
Breathalyzer test	X	X												
Immunogenicity (ADA) ¹⁴		X				X	X	X	X	X	X	X	X	X
Hypersensitivity Panel ¹⁵		X												
12-lead ECG ⁹	X													
Viral Serology ¹⁰	X													
PK samples ¹¹		X	X	X	X	X	X	X	X	X	X	X	X	X
MNA		X ¹⁶			X			X	X ¹⁷	X	X	X	X	X
Concomitant Medications ²	X	X	X	X	X	X	X	X	X	X	X	X	X	X
Randomization		X												
Study Drug Administration		X												
Future Use Sample ¹²		X				X		X						

Study Visit	Screening ¹	Baseline 01	Baseline 02	03	04	05 Cohort 1-3 Only	06	07	08	09	10	11	12	13 / Early Term	14 Cohort 4 Only
Study Day (Window)	-28 to -3	0	24 hr	48 hr	72 hr	4	8±1	15±1	30±1	45±3	60±3	90±3	120±3	180±3	
Counsel on the avoidance of pregnancy	X		X	X	X	X	X	X	X	X	X	X	X	X	X
Counsel on avoidance of botulinum toxin and vaccines	X		X	X	X	X	X	X	X	X	X	X	X	X	X
AE Review		X	X	X	X	X	X	X	X	X	X	X	X	X	X
SAE Review		X	X	X	X	X	X	X	X	X	X	X	X	X	X

1. Screening will be completed within 28 days prior to administration of study drug and may require more than one visit.
2. Concomitant medications including all of the following: prescription drugs, over-the –counter drugs, herbs, vitamins, nutritional supplements, illicit and recreational substance use, birth control information.
3. PE includes height and weight at screening.
4. Vital Signs to include sitting diastolic and systolic blood pressure, heart rate, and oral temperature. Vital signs will be checked just before injection and every visit.

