### 3.17 Vital Signs

Vital sign assessments including systolic and diastolic blood pressure (BP) [measured after sitting for at least 10 minutes], heart rate (HR), and oral temperature will be performed at each in-clinic study visit. Vital signs that are thought to be aberrant due to an error in measurement may be repeated. During screening and follow-up, a measurement that is a Grade 1 may be repeated once if the PI believes a transient condition led to the aberrant value.

Vital signs obtained at screening will serve as baseline values for the subject. Grade 1 values are allowable unless deemed clinically significant by the study investigator.

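### SAP 7.1 cuts baseline off at the dose date, which as written replaces the pre-dose Day 0 labs and physical examination with screening values and contradicts protocol 10.3.3.2 for labs

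*SAP*

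**What the plan says.** SAP 7.1 gives one general rule: "Baseline will be the latest available measurement prior to the study product dose date in each cohort". SAP 7.22.2 (labs) and 7.22.5 (physical examination) add no baseline of their own.

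The protocol is specific by variable. Section 10.3.3.2 calls for "Descriptive summary statistics for laboratory data at admission (baseline value) and each applicable post-injection visit" and, separately, "Descriptive summary statistics for vital signs at screening (baseline value) and each applicable post-injection visit". It names no baseline visit for the physical examination. SAP 3.17 agrees with the protocol on vital signs: "Vital signs obtained at screening will serve as baseline values for the subject".

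On timing, protocol 7.2 says that subjects are "admitted to the clinical unit the day of the injection and the following procedures will be performed prior to study drug administration". The list that follows includes "Perform abbreviated physical examination" and the clinical safety labs, both placed before randomization and injection. Screening runs from Day -28 to Day -3 (protocol 7.1).

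The baseline feeds a primary endpoint, change from baseline in physical examination, vital signs and safety labs after administration (protocol 3.2.1, SAP 2.2.1). It is reported in SAP Tables 14.3.5.1 to 14.3.5.4. SAP section 4 states that all its analyses are consistent with the protocol.

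**The concern.** A calendar-date cut-off excludes everything dated Day 0, including what was measured before the injection. The labs and examination closest to dosing would then not serve as the reference, and an older screening value would.

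Two consequences follow. First, an abnormality that arose between screening and the injection, and that persists afterwards, would be tabulated as a change following administration although no drug had been given when it appeared. Second, for labs, inclusion criterion 10 requires most screening chemistry to be within the reference range. A screening baseline is therefore selected to be normal, and some ordinary variation out of range shows up as a shift. The tables behind one primary endpoint would also depart from the protocol without the departure being declared.

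**Working it through.** **Applying the rule to the schedule.** The only input needed is the date of each assessment relative to the dose date.

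| Variable | Last pre-dose assessment | Baseline under SAP 7.1 as written | Baseline in protocol 10.3.3.2 | Result |
|---|---|---|---|---|
| Safety labs | Day 0, pre-dose | Screening (Day -28 to -3) | Admission | Conflict |
| Physical examination | Day 0, pre-dose | Screening | Not named | Same-day exam discarded |
| Vital signs | Day 0, just before injection | Screening | Screening | Agree |

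The SAP's own arithmetic in 7.1 works at the level of dates: study day is event date minus dose date, plus one when the event date is on or after the dose date. A pre-dose Day 0 draw gets the same study day as a post-dose one. Where the SAP means exposure rather than date, as in its treatment-emergent definition (3.15), it says so.

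**Size for labs.** The plan gives no figure to reproduce, so this part rests on stated assumptions:

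- Let X1, X2 and X3 be an analyte's standardized values at screening, pre-dose Day 0 and one post-dose visit. They are normal with equal pairwise correlation r, and there is no drug effect.
- The upper limit of normal (ULN) lies at c = +1.96 SD.
- Subjects are selected with X1 ≤ c.
- Nine analytes are counted, those that criterion 10 does not allow above ULN: calcium, sodium, creatinine, BUN, total bilirubin, AST, ALT, PT and PTT. Direct and indirect bilirubin and INR are left out because they overlap with total bilirubin and PT.
- There are 9 × 40 = 360 analyte-subject pairs, or 9 × 8 = 72 per arm of eight.

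Probability of an upward shift at the post-dose visit:

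- Screening baseline: P(X3 > c | X1 ≤ c)
- Day 0 baseline: P(X2 ≤ c, X3 > c | X1 ≤ c)
- Excess due to the rule: the difference, P(X2 > c, X3 > c | X1 ≤ c). These are subjects already high before dosing and still high afterwards.

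| r | Screening baseline | Day 0 baseline | Excess | Shifts in 360 pairs: screening / Day 0 / excess | Excess per 72 |
|---|---|---|---|---|---|
| 0.5 | 0.0209 | 0.0178 | 0.0031 | 7.5 / 6.4 / 1.1 | 0.2 |
| 0.7 | 0.0172 | 0.0132 | 0.0039 | 6.2 / 4.8 / 1.4 | 0.3 |
| 0.9 | 0.0104 | 0.0068 | 0.0036 | 3.8 / 2.5 / 1.3 | 0.3 |

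(Counts use unrounded probabilities.) Between 65% (2.5/3.8) and 85% (6.4/7.5) of the upward shifts remain under a Day 0 baseline: they are ordinary variation that no baseline rule removes. Adding the three overlapping analytes would scale the excess by 12/9, to about 1.5 to 1.9 in 40 subjects.

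**Size for the physical examination.** The documents give no rate of new findings between screening and Day 0, so no figure is offered.

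**The case against.** The best defence is that this is loose wording with an evident meaning. Protocol 7.2, protocol Table 2 and SAP Table 3-2 all label Day 0 as Baseline, and SAP 3.3 says that the check-in procedures come before drug administration. A programmer may well use date and time. This stands as evidence of intent, and it rules out the inference that Day 0 values are bound to be lost. It does not change what the rule says.

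The protocol is also not uniform on labs. Protocol 6.5.2, repeated in SAP 3.16, describes safety labs at screening and end of study and says that a Grade 1 value will act as the subject's baseline, which points towards screening. It also weakens the premise that every subject is within range at screening. Section 10.3.3.2 is nevertheless the analysis text, and it names admission. The mixed wording is a further reason for one explicit rule.

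A reader might infer larger effects, and the documents do not support them:

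- **Counting all 3.8 to 7.5 subject-analyte values that are normal at screening and high on Day 0 as errors.** That ignores how many upward shifts a Day 0 baseline would produce anyway. The net excess is 1.1 to 1.4.
- **Treating the pre-dose Day 0 draw or examination as a tabulated post-baseline visit.** Protocol 10.3.3.2 limits lab summaries to baseline and post-injection visits, and the endpoint covers changes after administration.
- **Putting a probability on false examination shifts.** Any such rate would be assumed with no basis in the documents.

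Finally, outputs are descriptive, nothing is tested, the rule applies equally to placebo, all results are listed, and new post-dose examination findings are reported as adverse events whatever the baseline. All of this stands and limits the importance of the point.

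**Conclusion.** SAP 7.1 is wrong as written for two of the three variables in this primary endpoint. For labs it contradicts protocol 10.3.3.2. For the physical examination it contradicts no stated protocol baseline, but it sets aside the same-day pre-dose examination for one 3 to 28 days old. Vital signs come out as both documents intend.

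The consequence is modest: about 1.1 to 1.4 extra upward lab shifts per post-dose visit in 40 subjects, or 0.2 to 0.3 in each active arm of eight and in the pooled placebo group, also eight. This rests on the assumed normal model, r between 0.5 and 0.9, nine analytes within range at screening, and no drug effect. Downward shifts are not counted. Adverse event and serious adverse event endpoints are unaffected. The point should be corrected because it concerns a primary endpoint and the correction is cheap, not because it threatens the trial's safety conclusions.

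**What to change.** In SAP 7.1, replace the baseline sentence with:

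*For clinical laboratory parameters and physical examination, baseline is the last assessment before the date and time of dosing (normally the pre-dose Day 0 assessment). For vital signs, baseline is the screening value.*

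The vital-sign clause is needed. Appendix A, footnote 4, says "Vital signs will be checked just before injection and every visit", so a blanket before-dosing rule would move that baseline to Day 0 and conflict with protocol 6.3 and 10.3.3.2 and with SAP 3.17.

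Also align the sentence in SAP 3.16 about Grade 1 lab values acting as baseline, so that it describes eligibility and does not set a second laboratory baseline.

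Cost: one replaced baseline statement and one aligned sentence in the SAP. The Day 0 labs and examination are already scheduled, so no procedure, visit or data item is added.

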### 7.2 Handling of Dropouts or Missing Data

All attempts will be made to collect all data per protocol. No imputation will be performed for missing values.

If the character result is reported for quantitative laboratory parameter then for summary and analysis it will be changed as follows into numerical value –

- a) If less than ‘<’ sign is used then the value will be reduced by 1 point from the last precision digit
- b) If greater than ‘>’ sign is used then 1 point will be added to the last precision digit.

Eg: if the lab parameter is reported to 2 decimal precision, <40.01 then for summary and analysis it will be treated as 40.00, if lab parameter is reported as whole number >40 then it will be considered as 41 and if the parameter is reported with 1 decimal precision <40.1 then it will be considered as 40.0.

### **7.2.1 Handling of missing/ incomplete dates for AE**

Imputation rules for missing or partial AE start date are defined below:

#### **If only Day of AE start date is missing:**

If the start date has month and year but day is missing, the first day of the month will be imputed

- If this date is earlier than the first dose date, then the first dose date will be used instead.
- If this date is later than the stop date (possibly imputed), then the stop date will be used instead.

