### **3.15 Adverse Events**

An AE is defined as any untoward medical occurrence in a subject administered a pharmaceutical product during the course of a clinical investigation. An AE can therefore be any

unfavorable and unintended sign, symptom, or disease temporally associated with the use of a study drug, whether or not thought to be related to the study drug.

A treatment-emergent AE (TEAE) is defined as any event not present before exposure to study drug or any event already present that worsens in either intensity or frequency after exposure to study drug.

An SAE is any untoward medical occurrence that at any dose:

- Results in death,
- Is life-threatening\*,
- Requires inpatient hospitalization or prolongation of existing hospitalization,
- Congenital anomaly/birth defect;
- Persistent or significant incapacity or substantial disruption of the ability to conduct normal life functions

*\*Life-threatening adverse event. An adverse event is considered “life-threatening” if, in the view of either the investigator or sponsor, its occurrence places the patient or subject at immediate risk of death. It does not include an adverse event, had it occurred in a more severe form, might have caused death.*

Subjects will be monitored throughout the study for AEs, from the time informed consent is obtained through End of Study (EOS). Any medical condition that is present at the time the subject is screened should be considered as baseline and not reported as an AE. However, if the condition increases in severity or frequency at any time during the study, it should be recorded as an AE.

All AEs must be graded for severity and relationship to study product based on the Investigator's assessment. AEs will be followed until resolution or stability even if this extends beyond the study-reporting period. Resolution of an AE is defined as the return to pretreatment status or stabilization of the condition with the expectation that it will remain chronic. Follow-up procedures, evaluations, and outcomes will be recorded on the subject's case report forms.

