#### **If Day and Month of AE start date are missing:**

If the start date has year, but day and month are missing, the 1st of January will be imputed

- If this date is earlier than the first dose date, then the first dose date will be used instead.
- If this date is later than the stop date (possibly imputed), then the stop date will be used instead.

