#### **If Year of AE start date is missing:**

If the year of AE start is missing or AE start date is completely missing, then imputation will not be done.

If the AE end date (full or partial) is before the first dose date, then the AE should be considered as a pre-treatment AE. Otherwise, the AE will be considered as TEAE.

Missing dates for Concomitant medication will be imputed similarly as described above for AE.

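### SAP 7.2.1 resets AE onset to the dose date even when the recorded month or year is wholly before dosing, so a known pre-dose AE that had not ended before dosing is counted as treatment-emergent

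*SAP*

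**What the plan says.** SAP 7.2.1 treats partial AE start dates in three blocks.

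- **Day missing:** "If the start date has month and year but day is missing, the first day of the month will be imputed". Two adjustments follow. The first is a floor: "If this date is earlier than the first dose date, then the first dose date will be used instead". The second is a cap: "If this date is later than the stop date (possibly imputed), then the stop date will be used instead".
- **Day and month missing:** "If the start date has year, but day and month are missing, the 1st of January will be imputed", with the same floor and cap.
- **Year missing:** no imputation. This block also holds the classification rule: "If the AE end date (full or partial) is before the first dose date, then the AE should be considered as a pre-treatment AE". It continues: "Otherwise, the AE will be considered as TEAE".

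The same date handling is extended to concomitant medications.

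SAP 3.15 gives the definition that these rules serve: "A treatment-emergent AE (TEAE) is defined as any event not present before exposure to study drug or any event already present that worsens" in intensity or frequency once exposed. SAP 7.22.1 restricts the AE summaries to events that begin or worsen after the dose. AE occurrence from administration to the final visit is a primary endpoint (SAP 2.2.1).

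**The concern.** A floor at the dose date is a sensible conservative choice when the missing part of the date leaves open whether onset came before or after dosing. The SAP does not limit it to that case. If the recorded month or year is earlier than that of dosing, onset is known to precede dosing, and the rule overrides that knowledge. The end-date sentence and the stop-date cap protect only AEs that ended before dosing. An AE that is ongoing, ends on or after dosing, or has no end date becomes a TEAE, and nothing requires that it worsened.

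Such an AE enters the tables that report the primary AE endpoint. Under the SAP 7.22.1 formula (onset date minus dosing date plus 1) it appears with onset on relative Day 1.

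**Working it through.** The plan states no figure on this point, so there is none to reproduce.

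**Step 1: apply the rule literally.** Order of operations: impute, floor at the dose date, cap at the stop date, then apply the end-date test. The dose dates are assumed for illustration.

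| Dose date | Recorded start | Recorded stop | Start under the rule | Class under the rule | Consistent with SAP 3.15? |
|---|---|---|---|---|---|
| 15-Apr-2021 | Mar-2021 | ongoing | 15-Apr-2021 | TEAE | No, unless it worsened |
| 15-Apr-2021 | Mar-2021 | 20-Apr-2021 | 15-Apr-2021 | TEAE | No, unless it worsened |
| 15-Apr-2021 | Mar-2021 | 25-Mar-2021 | 25-Mar-2021 | Pre-treatment | Yes |
| 15-Apr-2021 | Apr-2021 | ongoing | 15-Apr-2021 | TEAE | Order unknown; conservative |
| 15-Apr-2021 | Apr-2021 | 10-Apr-2021 | 10-Apr-2021 | Pre-treatment | Yes |
| 10-Jan-2021 | 2020 | ongoing | 10-Jan-2021 | TEAE | No, unless it worsened |
| 10-Jan-2021 | 2020 | 5-Jan-2021 | 5-Jan-2021 | Pre-treatment | Yes |

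The error is confined to rows where the known part of the start date is earlier than dosing and the AE did not end before dosing.

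**Step 2: how often a pre-dose onset falls in an earlier calendar month.** The screening window is Day -28 to Day -3 (Protocol 7.1). Assume dosing dates are spread evenly over a 365-day year. Every month has at least 28 days, so for a lag of L days (L from 1 to 28) onset falls in the previous month when dosing is on days 1 to L of a month. The share is 12L/365. With onset uniform over the last n days before dosing, the mean lag is (n + 1)/2 and the share is 12 × (n + 1)/2 ÷ 365.

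- All screened at Day -28, n = 28: 12 × 14.5/365 = 174/365 = 47.7%.
- Screening day s uniform from 28 to 3 days before dosing, constant onset rate from then to dosing: mean lag = Σ[s(s + 1)/2] ÷ Σs = 4056/403 = 10.06, and 12 × 10.06/365 = 33.1%.
- All screened at Day -14, n = 14: 12 × 7.5/365 = 90/365 = 24.7%.
- Onset in the last 7 days, n = 7: 12 × 4/365 = 48/365 = 13.2%.

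The year-only case needs screening to span a new year. With n = 28 the share is 14.5/365 = 4.0%.

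**Step 3: effect of one affected subject.** Each dose group has 8 active subjects (SAP Table 3-1). Placebo is pooled over four cohorts (SAP 7.1): 4 × 2 = 8. One subject with no other event in the same table row changes that row by 1/8 = 12.5 percentage points. A subject who already has an event in that row does not change the incidence.

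The documents do not say how many partial dates to expect, so no expected number of affected AEs can be given.

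**The case against.** The strongest counter-argument is that such records will hardly exist. SAP 3.15 does say that AEs are monitored from consent. But it also treats conditions present at screening as baseline, not as AEs. The AE and SAE review rows in Protocol Appendix A and SAP Table 3-2 start at Baseline, and the Day 0 procedures in Protocol 7.2 place AE assessment after administration. Medical history is updated on Day 0 (SAP 3.22), which gives a new pre-dose condition somewhere else to go. This stands, and it limits exposure to AEs that arise between screening and dosing, are unresolved at dosing or lack an end date, are recorded as AEs, and have a partial start date.

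A reader might also infer more than the documents support:

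- **That every AE with a known pre-dose start month or year becomes a TEAE.** The stop-date cap and the end-date rule return AEs that ended before dosing to pre-treatment status.
- **That about half of unresolved pre-dose AEs with a missing day are affected.** The 48% needs every subject screened on Day -28 and onset uniform over 28 days. Later screening lowers it, and unresolved events tend to be recent.
- **That the comparison of active with placebo is biased.** Randomisation follows Day 0 admission and is double-blind (Protocol 4.2.1), so pre-dose onsets should not differ systematically by arm. The error inflates counts in all groups, though with 8 per group chance imbalance is possible.
- **That causality calls or dose escalation are distorted.** Causality is the investigator's assessment (Protocol 8.2.2). The Safety Review Committee works from data that are neither monitored nor coded (Protocol 8.5.3 and 8.6.4), and nothing says that SAP-imputed dates reach it.
- **That medication results change.** Medications are only listed (SAP 7.14 and 7.22.6).

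None of this removes the contradiction. Whenever such a record occurs, the rule gives the wrong class unless the AE worsened after dosing.

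**Conclusion.** The point holds in limited form. Read as written, SAP 7.2.1 discards known information about onset and counts a pre-dose AE that did not end before dosing as treatment-emergent, contrary to SAP 3.15 and 7.22.1. The number of affected records is probably small. The range of 13% to 48% for onsets in an earlier month rests on the assumptions in the working about screening day, onset timing and dosing dates. The 12.5 points rest on a subject with no other event in that row. The direction is over-counting, expected in active and placebo alike.

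The scope of the end-date rule is also unclear, because it stands under the heading for a missing year. Even if it were confined to that heading, the cap in the other two blocks would give a pre-dose start when the stop date is known. However, the cap mentions an imputed stop date, and SAP 7.2.1 gives no rule for imputing one.

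This ranks between a minor point and one that should be corrected: low exposure, but a stated rule that contradicts its own definition in a primary safety output and is cheap to repair.

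**What to change.** Amend SAP 7.2.1 as follows.

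1. Apply the dose-date floor only when the known month and year equal those of dosing (day missing), or the known year equals the dosing year (day and month missing).
2. If the known part is earlier, keep the pre-dose date and class the AE as pre-treatment unless it worsens after dosing.
3. State that the end-date rule covers all partial and missing start dates, not only those with a missing year. It must not be narrowed to completely missing start dates. For example, take a dose on 15-Apr-2021, a start of 2021 and an end of Mar-2021. The year matches, so the floor still applies, and without the end-date rule the AE could become a TEAE.
4. Use the same date rule for medications for consistency; only listings change.

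In the worked dates, this changes the three inconsistent rows to pre-treatment (absent worsening) and leaves the other four as they are. The cost is two or three sentences in the SAP and a small programming change, with no effect on data collection.
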